6.2. Preparation/Handling/Storage/Accountability

The investigator or designee must confirm appropriate temperature conditions have been maintained during transit for all study intervention received and any discrepancies are reported and resolved before use of the study intervention.

[REDACTED]
AGN-190584

Only participants enrolled in the study may receive study intervention, and only authorized site staff may supply or administer study intervention. All study intervention must be stored in a secure, environmentally controlled, and monitored (manual or automated) area in accordance with the labeled storage conditions with access limited to the investigator and authorized site staff. All study intervention must be stored upright, in a refrigerator, and protected from freezing.

[REDACTED]

Participants will be instructed on the proper storage of study intervention and to keep it out of the reach of children at all times.

[REDACTED]

6.3. Measures to Minimize Bias: Randomization and Blinding

All participants will be centrally assigned to randomized study intervention using the IxRS. Randomization and kit assignment will be conducted on Day 1 (baseline). At Day 1, participants will be randomized in a 1:1 ratio into 1 of the 2 study groups. This randomization will be stratified by age (2 groups: ≤ 50 years and > 50 years), baseline binocular DCNVA (2 groups: 20/40 to 20/60 inclusively, and worse than 20/60), iris color (brown and non-brown), and emmetropes/non-emmetropes. A maximum of 50% (100 per arm) of the participants enrolled will have brown iris color, and a maximum of 25% (50 per arm) of the participants will be non-emmetropes (a sphere outside of -0.50 D to +0.75 D and/or a cylinder greater than 0.75 D).

AGN-190584

6.5. Concomitant Therapy

The use of any concomitant medication, prescription or over-the-counter, is to be recorded on the participant's eCRF at each visit along with the reason the medication is taken.

From screening to the EOS, site staff will question each participant specifically on the use of concomitant medications. Site staff must notify the sponsor immediately if a participant consumes any concomitant medications not permitted by the protocol. Participants who used prohibited concomitant medications may be discontinued from the study at the discretion of the investigator or the sponsor.

6.5.1. Prohibited Interventions and Washout Before the Study

Use of medications that may have a substantial effect on visual function or the optical properties of the eye is prohibited 2 weeks prior to Day 1 visit and during the study:

- systemic medications with potential ocular side effects, including topiramate, hydroxychloroquine, ethambutol, phosphodiesterase 5 inhibitors (sildenafil, vardenafil, tadalafil), or tamoxifen
- ophthalmic, systemic, or intranasal anticholinergics and α -adrenergic receptor agonists with potential pupillary or accommodative effects, including oxymetazoline, pilocarpine, tetrahydrozoline, phenylephrine, naphazoline, cyclopentolate, atropine, beta-blockers, or antihistamines
- systemic maprotiline, tricyclic antidepressants, or monoamine oxidase inhibitors

AGN-190584

6.5.2. Permitted Interventions

Any medication or vaccine (including over-the-counter or prescription medicines, vitamins, and/or herbal supplements) that the participant is receiving at the time of enrollment or receives during the study must be recorded along with:

- Indication
- Dates of administration including start and end dates
- Dosage information including dose and frequency

Therapy considered necessary for the participant's welfare may be given at the discretion of the investigator. If the permissibility of a specific medication/intervention is in question, please contact the sponsor.

The sponsor or designee should be contacted if there are any questions regarding concomitant or prior therapy.

The concurrent use of nonocular medications that do not have a substantial effect on the pupil, accommodative properties, or retinal function of the eye will be permitted during the study if a stable dosing regimen is established. The dosing regimen is not considered to be stable if a participant starts, stops, or changes the dose/drug during the study.

Any medication taken during the study between the date of the first dose of study intervention and the date of the EOS visit will be recorded in the eCRF as a concomitant medication; any medication started after the EOS visit will not be considered a concomitant medication and should not be captured in the eCRF.

6.5.3. Rescue Medicine

Rescue medicine is not applicable.

6.5.4. Prohibited Interventions During the Study

Use of ocular medications other than study intervention or medications administered to conduct study procedures are prohibited from the screening visit until study exit.

The decision to administer a prohibited medication/treatment will be made with the safety of the study participant as the primary consideration. When possible, Allergan should be notified before the prohibited medication/treatment is administered.

6.6. Dose Modification

Dose modification is not applicable.

6.7. Intervention after the End of the Study

No interventions after the end of the study are planned.

AGN-190584

7. **Discontinuation of Study Intervention and Participant Discontinuation/Withdrawal**

A premature discontinuation will occur if a participant who signs the ICF and is dosed ceases participation in the study, regardless of circumstances, before the completion of the protocol-defined study procedures.

Reasons for discontinuation from the study intervention and/or the study may include the following:

- AE
- Lack of efficacy
- Lost to follow-up
- Noncompliance with study drug
- Physician decision
- Pregnancy
- Protocol deviation
- Site terminated by sponsor
- Study terminated by sponsor
- Withdrawal by subject
- Death
- Other

7.1. **Discontinuation of Study Intervention**

See the SoA (Section 1.3) for data to be collected at the time of early exit.

Participants who discontinue the study intervention early will be encouraged to stay in the study for the safety assessments at Day 30.

7.2. **Participant Discontinuation/Withdrawal from the Study**

- A participant may withdraw from the study at any time at his/her own request or may be withdrawn at any time at the discretion of the investigator for safety, behavioral, compliance, or administrative reasons.

AGN-190584

- If the participant withdraws consent for disclosure of future information, the sponsor may retain and continue to use any data collected before such a withdrawal of consent.
- If a participant withdraws from the study, he/she may request destruction of any samples taken and not tested, and the investigator must document this in the site study records.
- See the SoA (Section 1.3) for data to be collected at the time of early exit.

7.3. Lost to Follow Up

A participant will be considered lost to follow-up if he or she repeatedly fails to return for scheduled visits and is unable to be contacted by the study site.

The following actions must be taken if a participant fails to return to the clinic for a required study visit:

- The site must attempt to contact the participant and reschedule the missed visit as soon as possible and counsel the participant on the importance of maintaining the assigned visit schedule and ascertain whether or not the participant wishes to and/or should continue in the study.
- Before a participant is deemed lost to follow-up, the investigator or designee must make every effort to regain contact with the participant (where possible, 3 telephone calls and, if necessary, a certified letter to the participant's last known mailing address or local equivalent methods). These contact attempts will be documented in the participant's medical record.
- Should the participant continue to be unreachable, he/she will be considered to have withdrawn from the study.

AGN-190584

8. Study Assessments and Procedures

- Study procedures and their timing are summarized in the SoA (Section 1.3). Protocol waivers or exemptions are not allowed.
- Immediate safety concerns should be discussed with the sponsor promptly upon occurrence or awareness to determine if the participant should continue or discontinue study intervention.
- Adherence to the study design requirements, including those specified in the SoA, is essential and required for study conduct.
- All screening evaluations must be completed and reviewed to confirm that potential participants meet all eligibility criteria. The investigator will maintain a screening log to record details of all participants screened and to confirm eligibility or record reasons for screening failure, as applicable.
- Procedures conducted as part of the participant's routine clinical management (eg, blood count) and obtained before signing of the ICF may be utilized for screening or baseline purposes provided the procedures met the protocol-specified criteria and were performed within the timeframe defined in the SoA.

8.1. Efficacy Assessments

Efficacy assessments are: mesopic and photopic, high contrast DCNVA for each eye and binocularly, mesopic and photopic, high contrast DCIVA for each eye and binocularly, PRO questionnaires (NVPTQ, PICQ,

AGN-190584

Table 8-1 Efficacy Assessments

Assessment	Timing	Measurement
Visual Acuity		
Mesopic, high contrast DCNVA for each eye and binocularly	
 • Screening • Days 1, 14, and 30: Hours 0, 0.25, 0.5, 1, 3, 6, 8, and 10 • Days 3 and 7: Hours 0, 1, and 3 	
 • Visual acuity for near (40-cm), intermediate (66-cm) and distance (4-meter) targets will be measured in mesopic and photopic conditions. • Mesopic condition is defined as lighting 3.2 to 3.5 candelas per square meter (cd/m^2; 10 to 11 lux) measured at the target. Photopic condition is defined as lighting $\geq 80 \text{ cd}/\text{m}^2$ (251 lux) measured at the target.
Photopic, high contrast DCNVA for each eye and binocularly	
 • Screening • Days 1, 14, and 30: Hours 0, 0.25, 0.5, 1, 3, 6, 8, and 10 • Days 3 and 7: Hours 0, 1, and 3 	
Mesopic and photopic, high contrast DCIVA for each eye and binocularly	
 • Screening • Days 1, 14, and 30: Hours 0, 1, 3, 6, 8, and 10 • Days 3 and 7: Hours 0, 1, and 3 	

AGN-190584

8.2. Safety Assessments

Planned timepoints for all safety assessments are provided in the SoA (Section 1.3).

8.2.1. Vital Signs

Vital signs will be assessed as follows:

- Blood pressure and pulse rate will be assessed.
- Systolic and diastolic blood pressure will be measured using an appropriate sphygmomanometer after participants have been at rest (seated) for at least 5 minutes. Blood pressure will be recorded in mm Hg.
- Heart rate will be measured in bpm after the participant has been in a resting state (seated) for at least 5 minutes. Pulse will be counted for 30 seconds, multiplied by 2, and recorded in bpm.
- Blood pressure and pulse measurements will be assessed with a completely automated device. Manual techniques will be used only if an automated device is not available. Manual techniques will be used only by adequately trained personnel; whenever possible, the same person should perform all manual assessments as much as possible.
- Participants should refrain from smoking or ingesting caffeine during the 30 minutes preceding the measurement.

8.2.2. Pregnancy Testing

Pregnancy test kits will be provided by the investigator and will be administered according to the instructions provided with the tests. WOCBP must have a negative test result before receiving

AGN-190584

study intervention. This test will also be performed at the Day 30 (Early Exit) visit, and may be performed at any other visit, at the investigator's discretion. At each visit, the investigator should discuss contraceptive use compliance with WOCBP. Additional details are provided in [Appendix 6](#).

8.2.3. Photopic and Mesopic, High Contrast Corrected Distance Visual Acuity for Each Eye and Binocularly

Photopic and mesopic, high contrast CDVA, for each eye and binocularly, will be assessed using the provided visual acuity charts for distance vision in a room with mesopic lighting conditions (defined by lighting 3.2 to 3.5 candelas [cd]/m² [10 to 11 lux] measured at the target) and photopic lighting conditions (defined by lighting ≥ 80 cd/m² [251 lux] measured at the target). Forced choice letter by-letter scoring will be used for each test and the total number of correct letters or the highest value (number) of the grid identified (as applicable) will be recorded. Further details are outlined in the Procedure Manual.

8.2.4. Near Contrast Sensitivity

Near contrast sensitivity assessment will be conducted under photopic conditions. A Pelli-Robson contrast sensitivity chart will be used. The logarithmic contrast sensitivity value of the last triplet of which at least 2 letters are correctly read is marked as the contrast sensitivity. Further details are outlined in the Procedure Manual.

8.2.5. Study Intervention Tolerability and Drop Comfort Assessments

The presence and severity of ocular symptoms will be elicited from the participant for both eyes after dosing. Symptoms, including blurred vision, foreign body sensation, pain, burning/stinging, tearing, and itching, will be classified using a 5-point grading scale with 0 = none, +0.5 = trace, +1 = mild, +2 = moderate, and +3 = severe. The duration of symptoms (< 1 minute, 1 to 5 minutes, > 5 minutes) will be captured once immediately after the second eye is instilled with a drop of study intervention. If any other ocular symptoms are present, these will also be captured.

Participants will be asked to rate the overall comfort of the eye drops using a 6-point scale (ie, soothing, very comfortable, comfortable, uncomfortable, very uncomfortable, and intolerable) immediately after the second eye is instilled with a drop of study intervention, for both eyes.

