### **5.6.6. Study Intervention Tolerability and Drop Comfort Assessments**

Ocular tolerability assessment will be performed at each visit. Symptoms of blurred vision, foreign body sensation, pain, burning/stinging, tearing, and itching will be assessed using a 5-point scale (0 = none, 0.5 = trace, 1 = mild, 2 = moderate, and 3 = severe) for the severity and a 3-point scale (<1 min, 1 to 5 min, and >5 min) for the duration. Drop comfort will be assessed using a 6-point scale (soothing, very comfortable, comfortable, uncomfortable, very uncomfortable, and intolerable). For the severity, duration, and drop comfort, the number and percentage of participants in each category will be tabulated for each time point by treatment group.

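### Symptom duration, on a scale reaching over 5 minutes, is captured once immediately after the second drop; read literally, the longest category cannot be recorded

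*Protocol*

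**What the plan says.** Protocol 8.2.5 uses three timings for the post-dose questions.

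- Presence and severity have a loose anchor: "The presence and severity of ocular symptoms will be elicited from the participant for both eyes after dosing".
- Duration has three categories, beginning with under 1 minute, and a tight anchor: "1 to 5 minutes, > 5 minutes) will be captured once immediately after the second eye is instilled".
- Overall drop comfort has the same tight anchor: "immediately after the second eye is instilled with a drop of study intervention, for both eyes".

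Protocol 8.2 refers timing elsewhere: "Planned timepoints for all safety assessments are provided in the SoA". That schedule is redacted in the public copies of both the protocol (Section 1.3) and the SAP (Tables 1-1 and 1-2).

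SAP 5.6.6 says "Ocular tolerability assessment will be performed at each visit" and repeats the scale as "a 3-point scale (<1 min, 1 to 5 min, and >5 min) for the duration". The planned output is descriptive: "For the severity, duration, and drop comfort, the number and percentage of participants in each category will be tabulated for each time point by treatment". The SAP gives no time of capture and does not say how a symptom still present at the time of asking is coded.

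**The concern.** A duration can be recorded only once it has elapsed. An anchor immediately after instillation suits a comfort rating but not a scale whose top category begins at 5 minutes. The word once also rules out the obvious repair, which would be to ask again later.

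Tolerability is listed under the safety objective, and an acceptable safety and tolerability profile is one of the two clinical hypotheses in Protocol 4.1.1. For symptoms such as blurred vision, pain and burning or stinging, persistence is part of what a reader wants from the table. If symptoms still present are cut off at the time of asking, they fall into the shortest category. If each of the roughly 50 sites finds its own way round the wording, the categories will not mean the same thing across sites.

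**Working it through.** The plan states no figure on this point, so there is none to reproduce. The check compares the capture time with the scale.

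**Inputs**

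- Categories: under 1 minute, 1 to 5 minutes, over 5 minutes (Protocol 8.2.5; SAP 5.6.6).
- Capture: once, immediately after the second-eye drop (Protocol 8.2.5).
- c = delay in minutes between the second drop and the question. Literally c is about 0. The range shown, 0 to 5.5, is an assumption.
- g = gap in minutes between the first-eye and second-eye drops. The readable text does not give it. The range shown, 0 to 2, is an assumption.

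**Formula**

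A symptom caused by the drop cannot begin before the drop. The longest duration that can have been observed when the question is asked is therefore:

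- second eye: c
- first eye: g + c

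**Results: longest category that can be observed**

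| g | c | First eye, g + c | Second eye, c |
|---|---|---|---|
| 0 | 0 | 0: under 1 min | 0: under 1 min |
| 0.5 | 0 | 0.5: under 1 min | 0: under 1 min |
| 1 | 0 | 1: 1 to 5 min | 0: under 1 min |
| 2 | 0 | 2: 1 to 5 min | 0: under 1 min |
| 2 | 1 | 3: 1 to 5 min | 1: 1 to 5 min |
| 0 | 5 | 5: 1 to 5 min | 5: 1 to 5 min |
| 2 | 5 | 7: over 5 min | 5: 1 to 5 min |
| 0 | 5.5 | 5.5: over 5 min | 5.5: over 5 min |

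**Reading the table**

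1. On the literal reading (c about 0), the second eye can show only the shortest category, whatever the gap.
2. On the same reading, the first eye reaches 1 to 5 minutes only if g is at least 1 minute. It does not reach over 5 minutes for any assumed gap up to 2 minutes.
3. The top category becomes observable in the first eye when g + c exceeds 5 minutes, and in the second eye only when c itself does. A question more than 5 minutes after the second drop therefore works for both eyes whatever g is.

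**Existing assessments after 5 minutes**

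Table 8-1 in Protocol 8.1 lists near-acuity testing on "Days 1, 14, and 30: Hours 0, 0.25, 0.5, 1, 3, 6, 8, and 10". Hour 0.25 is 0.25 × 60 = 15 minutes. On Days 3 and 7 the same table shows only Hours 0, 1 and 3, so the first post-dose time there is 60 minutes. Attaching the question to the first listed post-dose assessment would give 15 minutes of recall at some visits and 60 at others, in a table reported by time point.

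**The case against.** The strongest reply is that the controlling text cannot be seen. Protocol 8.2 sends all safety timepoints to the Schedule of Activities, which is redacted, and the text of Section 6.1.2 on administration is not readable either. A workable time may be set in one of them. This stands as far as it goes, and the redaction is not counted against the plan. But a later time in the schedule would conflict with the plain wording of 8.2.5, so the two would still have to be reconciled.

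Three stronger readings are tempting, and the documents do not support them.

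- **A reader might infer that two of the three categories are unobservable in both eyes.** That holds for the second eye. In the first-dosed eye the middle category can be reached if the unstated gap is at least 1 minute.
- **A reader might infer that the table will understate duration.** That requires every site to follow the wording literally. Staff may take the phrase as naming the instillation being rated and wait until the symptom ends; participants may estimate; the field may be left blank. The result could be correct data, noise, missing values or understatement.
- **A reader might infer a bias towards no difference between arms.** That needs literal conduct and also longer-lasting symptoms in one arm. The readable text gives no data on either, and SAP 5.6.6 plans counts and percentages, not a test.

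Persistent symptoms are also not lost to the safety evaluation. Adverse events are collected until 30 days after the last dose (Protocol 8.3.1) and tabulated by severity and causality (SAP 5.6.2). Headache has its own visual analog scale (SAP 5.6.7), and distance acuity and slit-lamp findings are summarized separately (SAP 5.6.4, 5.6.5 and 5.6.9). This stands, and it keeps the point small.

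**Conclusion.** The inconsistency is real and minor. Protocol 8.2.5 states a rule which, followed as written, cannot record a duration over 5 minutes in either eye or a duration of 1 to 5 minutes in the second eye, and SAP 5.6.6 does not repair it. The duration part of the tolerability table may therefore understate duration or contain guessed or missing values; which of these occurs cannot be determined from the documents.

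The conclusion for the first eye assumes a gap between eyes of no more than about 2 minutes. The whole conclusion assumes that the redacted schedule does not override the sentence. One descriptive field is affected. No efficacy or safety hypothesis test, significance level or sample size depends on it.

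**What to change.** - In Protocol 8.2.5, leave the drop comfort rating at instillation. Record duration once, at a single common time more than 5 minutes after the second drop, the same at every visit; about 15 minutes is one example. Provide an answer for a symptom still present, counted as over 5 minutes.
- Repeat the capture time and that coding in SAP 5.6.6.
- Check the Schedule of Activities. If it already sets a workable time, bring 8.2.5 into line with it.
- If data have already been collected under the present wording, state in the SAP how ongoing symptoms were coded and note the limitation under the table.

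The cost is one sentence in each document and a change of timing on the form, with no new visit. Participants would have to recall, over a short interval, symptoms that have already ended. On Days 3 and 7 the readable efficacy schedule has no Hour 0.25 assessment, so a 15-minute question would be one added form timing on those days. Using Hour 1 there would avoid the addition, but recall would then differ between visits.

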8.2.6. Temporal/Supraorbital Headache Visual Analog Scale

Participants will be asked to rate the degree of temporal and supraorbital headache experienced after the second eye is instilled with a drop of study intervention, for the right and left eyes separately. Headache will be reported on an unmarked 100-mm wide VAS, ranging from no pain on the left to worst possible pain on the right.

[REDACTED]
AGN-190584**8.2.7. Intraocular Pressure**

IOP must be measured after the biomicroscopic exam is completed and prior to pupil dilation. Measurements will be taken using a Goldmann applanation tonometer affixed to a slit-lamp with the participant seated. The participant and slit-lamp should be adjusted so that the participant's head is firmly positioned on the chin rest and against the forehead rest without leaning forward or straining. Tight fitting neckwear should be loosened. Both eyes will be tested, with the right eye preceding the left eye. The measurer will look through the binocular viewer of the slit lamp at low power. The tension knob will be preset at a low-pressure value (4 to 6 mm Hg). The measurer will follow the image of the fluorescein stained semicircles while slowly rotating the tension knob until the inner borders of the fluorescein rings touch each other at the midpoint of their pulsation in response to the cardiac cycle. When this image is reached, the measurer will take his/her fingers off the tension knob and record the IOP reading along with the date and time of day.

